8.2.2 Urine Drug Screen (UDS)

Urine samples will be collected at every clinic visit using FDA-approved one-step temperaturecontrolled urine drug test cups following all of the manufacturer's recommended procedures. The UDS will test for the presence of opiates, oxycodone, barbiturates, benzodiazepines, cocaine, amphetamines, MA, marijuana, methadone, and Ecstasy (MDMA). A validity check may be performed using a commercially available adulterant test strip that indicates normal ranges for creatinine, pH (at minimum), nitrate, glutaraldehyde, specific gravity, bleach and pyridinium chloromate. Study staff may observe the collection of UDS. In the event of suspected tampering, the study team will request a second sample and may observe the urine collection process according to clinic standard operating procedures.

8.2.3 Visual Analog Craving Scale (VAS)

Participants' opioid craving will be documented on a visual analog scale (VAS) that ranges from 0 (no craving) to 100 (most intense craving possible). The VAS will be completed at screening and at each Medical Management and assessment visit.

8.2.4 DSM-5 Checklist/Modified CIDI

The DSM-5 Checklist is a semi-structured interviewer administered instrument that provides current diagnoses for substance use disorders based on DSM-5 diagnostic criteria. The CIDI will be modified for use in this study. Either/both measures will be completed at screening to determine presence and severity of opioid use disorder, and at 6 months as the primary outcome.

8.2.5 HIV-Gain

The HIV-Gain will be used to assess HIV risk. It will be administered at screening and at assessment visits.

8.3 Crime and Recidivism

8.3.1 Arrest Records

Arrest records will be accessed to compile information on participants' arrests, convictions, sentences, and incarcerations.

8.3.2 CJ-DATS Crime Grid

Criminal Justice history will be documented including information about criminal activity, arrests, convictions, and incarcerations with this 24-item section of the CJ-DATS intake instrument.

8.4 Data Collection and Management

Study measures will be collected using electronic data entry, and managed by ISAP's Data Management Center (DMC) to manage large amounts of data. This process performs range checks and other verification procedures during and immediately after completion of data entry, thus ensuring the reliability of de-identified data transmitted to our DMC via a secure server at the end of each day. Upon study completion, each participant's data record is saved to disk and securely stored.

8.5 Data Sharing

The project will comply with NIH regulations regarding provision of access to the data set (in nonidentifiable form) after study completion. As approved by the PI, the ISAP DMC will respond to requests for data. Articles from the project will be made available via submittal to PubMedCentral after publication.

9.0 TRAINING

The study staff will be trained and certified as specified in the study Training Plan. Training will cover standard human subject training (e.g., Good Clinical Practices), as well as protocol-specific training as needed (e.g., assessments, study interventions, fidelity to the protocol and safety procedures, data management and collection, research procedures including understanding reliability and validity, and problem solving). Study Medical staff will be trained on all aspects of medication induction and delivery.

10.0 STATISTICAL ANALYSES

The project emphasizes evaluation of the clinical utility of Vivitrol in jail inmates as compared with a Drug Education condition (DE), while descriptive statistics will provide an overall assessment of the implementation of the protocol.

Analyses will include an Intent-to-treat (ITT) design such that all randomized participants who received at least one dose of medication (VI, PNV), or received at least one session of drug education (DE) will be included who did not violate the protocol in a way that could potentially affect the efficacy results. Participants will be excluded from the Protocol Population (PP) if:

- 1. concomitant medication that is known to have significant clinical effect on primary or secondary endpoints was administered.
- 2. Violations of the inclusion or exclusion criteria are judged to affect the efficacy evaluations.

Subjects in the PP population will be allocated to treatment groups in the analysis based on the actual treatment they received. If there is substantial difference between the ITT population and the PP population, all analyses described below will be performed using only subjects in this group.

All statistical tests will be performed using two-sided .05 significance levels, unless otherwise stated. All comparisons between treatments will be reported with parameter estimates and 95% confidence intervals. For parameters measured at baseline and subsequently, the variables of interest are changes from baseline.

Post-baseline variables will not be imputed; estimates can be obtained using the hierarchical models specified below under the assumption of missing at random. For the primary outcome measure, diagnosis at six months, subjects who have dropped out for whatever reason will be considered to retain the diagnosis. Other outcome measures for which data are missing will be imputed using multiple imputation methods. Sensitivity analyses will repeat specific analyses using permutation tests of at least 1000 samples.

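### The set labelled ITT is a modified ITT set with no all-randomised analysis behind it, and the rule for moving to the per-protocol set has no defined trigger or consequence

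*Combined protocol and SAP*

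**What the plan says.** Section 10.0 announces an intent-to-treat design and then includes "all randomized participants who received at least one dose of medication (VI, PNV), or received at least one session of drug education (DE"). The same sentence adds a second condition, that these are participants "who did not violate the protocol in a way that could potentially affect the efficacy results".

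Section 7.3 fits the first condition. A participant who leaves before induction, or the matching point for a behavioural assignment, is replaced. Only those who leave later count as failures.

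On the per-protocol (PP) set, section 10.0 says: "Subjects in the PP population will be allocated to treatment groups in the analysis based on the actual treatment they received". It continues: "If there is substantial difference between the ITT population and the PP population", then "all analyses described below will be performed using only subjects in this group".

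For the diagnosis outcome, "subjects who have dropped out for whatever reason will be considered to retain the diagnosis".

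On enrolment, section 5.4 recruits until 150 people have been randomised. Section 10.3 plans 50 per condition.

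**The concern.** Intention-to-treat protects the comparison because membership of the set is fixed at randomisation. Here it depends on something that happens afterwards, in a trial that section 7.14 describes as unblinded. If people who never start differ from those who do, and the share lost differs between arms, the arms compared are no longer the arms randomised.

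The rule that dropouts keep the diagnosis does not repair this, because a participant with no first dose or session is outside the set to which it applies. Section 10.4.2 plans to describe reasons for refusal after randomisation, but it does not return these people to the efficacy comparison.

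The switch rule is a second, separate weakness. It gives no measure of difference, no threshold, no timing and no decision-maker. As worded, it permits every analysis to move to a comparison grouped by treatment received rather than by randomisation.

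**Working it through.** **Is there an all-randomised analysis anywhere?** Section 10.0 requires a first dose or session. Section 7.3 replaces those without one. Section 10.4.2 specifies the model and contrast but no other population. So no such analysis is defined.

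**Can loss before the start differ by arm?** There are two routes.

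- *Refusal after assignment.* The trial is open-label, so a participant can leave on learning the arm. This is possible in any arm, and no section quantifies it.
- *Naloxone challenge.* Abstract section 2.4 (Interventions) and section 11.23 describe it only for those receiving Vivitrol. Section 7.4.1, Step 4, ends participation after a failed repeat challenge. Abstract section 2.4 and section 5.2 suggest that randomisation comes first. Section 7.2 randomises only once all assessments are in and eligibility is confirmed. Section 7.4.1 places eligibility assessments inside pre-induction (Step 3) and treats a failed repeat challenge as an eligibility matter (Step 4). The order is unresolved.

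**How large could the effect be?** The documents give neither a non-start rate nor an expected rate of opioid use disorder (OUD), so every input here is an assumption: VI versus DE only, no drug effect, true OUD rate p = 0.60 in both arms, 50 randomised per arm and only starters analysed. Let x be the share of VI who never start and q their OUD rate. DE loses nobody unless stated.

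Rate among VI starters = (p − xq)/(1 − x). Rejection is by exact binomial enumeration of a two-sided 0.05 pooled z-test.

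| x | q | VI starters' rate | Difference from DE (0.600) | n analysed | Rejection |
|---|---|---|---|---|---|
| 0 | – | 0.600 | 0 | 50 v 50 | 5.2% |
| 0.05 | 0.90 | (0.60 − 0.045)/0.95 = 0.584 | 1.6 points favouring VI | 48 v 50 | 5.6% |
| 0.10 | 0.80 | (0.60 − 0.08)/0.90 = 0.578 | 2.2 points favouring VI | 45 v 50 | 5.3% |
| 0.20 | 0.90 | (0.60 − 0.18)/0.80 = 0.525 | 7.5 points favouring VI | 40 v 50 | 11.4% |
| 0.20 | 0.30 | (0.60 − 0.06)/0.80 = 0.675 | 7.5 points against VI | 40 v 50 | 11.2% |

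(In the 5% row, 47.5 starters is rounded to 48.) If DE loses the same share with the same q, both rates shift equally and the difference is 0 points.

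**Would scoring every non-starter as still diagnosed be enough?** Analyse all 50 per arm, reach a share r of VI non-starters, and score the rest as having OUD. Error = x(1 − q)(1 − r).

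- Reversal case (x = 0.20, q = 0.30): r = 0 gives 0.20 × 0.70 = 14.0 points and 31.7% rejection; r = 0.5 gives 7.0 points and 11.2%; r = 1 gives 0 points and 5.2%. The like-for-like figure for the present plan is 11.2%.
- x = 0.20, q = 0.90, r = 0: 0.20 × 0.10 = 2.0 points, against 7.5 under the present plan.

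So the rule alone can improve on the present plan or do worse than it.

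**Enrolment.** Assume 10-20% non-start in VI and PNV only, with 50 starters wanted in each arm.

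- Replacement within the arm that lost the participant: 50 + 2 × 50/(1 − x) = about 161 (x = 0.10) or 175 (x = 0.20) randomised.
- The 1:1:1 urn simply continues: 3 × 50/(1 − x) = about 167 or 188.
- Stopping at 150 randomised: 150 − 100x = 140 or 130 in the set now called ITT.

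**The case against.** The strongest reply concerns strength, not the definition.

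**Size.** At 5-10% loss the illustration barely moves from 5.2%. Roughly doubling it takes 20% loss in VI, none in DE, and non-starters whose OUD rate is 30 points from the average. The primary contrast in section 10.4.2 also pools data from other sites, which the illustration does not model. Section 10.3 presents the trial as preliminary to a larger one. All of this stands, so the case rests on the definition and not on these numbers.

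**Challenge failure.** A reader might infer that it removes people selectively from the medication arms. The documents do not establish this. If the challenge precedes randomisation, that route disappears. Candidates are already detoxified (sections 5.3 and 5.4), and a failed first challenge may be repeated. What remains is refusal after open-label assignment and the missing all-randomised analysis.

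**The switch.** A reader might infer that the analysis set will be chosen after outcomes are seen. Section 10.0 does not say so: the difference could be in membership rather than results, and the PP run might be an added one. It does not exclude the stronger reading either. An undefined trigger with an unclear consequence is as far as the text goes.

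**The violator clause.** It may be PP wording placed in the wrong sentence, so it calls for clarification rather than a finding that violators are meant to be removed from ITT.

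**The enrolment count.** The 150 may be meant as the number after replacement. That needs one sentence in the protocol.

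**Conclusion.** The point holds in this form. The set labelled ITT is a modified ITT set, and no all-randomised, as-assigned analysis is defined. The rule for moving to another set has no defined trigger and an unclear consequence, most naturally the as-treated PP set. Both conclusions follow from the wording and need no assumption about loss rates.

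The bias itself is unquantified. Its direction is unknown, it is small in the illustration at 5-10% non-start, and it is zero when loss is equal and alike in both arms. The documents do not support a claim that the trial is biased towards medication, or biased by a large amount. The matter still has to be fixed before analysis, because it concerns the primary population and because month-6 data never sought from non-starters cannot be recovered later.

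**What to change.** 1. Make the primary set all randomised participants in their assigned arm. Keep the present set as a secondary set labelled modified ITT. Clarify whether the violator clause belongs to the PP definition.
2. Delete the switch sentence and report PP as supportive only.
3. Keep replaced participants in the all-randomised set and tabulate non-starts by arm with reasons, which section 10.4.2 already plans to describe. State whether the 150 in section 5.4 counts those randomised or those who start after replacement, and how replacements are allocated.
4. By IRB-approved amendment (section 11.2), seek the month-6 assessment from consenting non-starters. Section 7.13 lets those who opt out of medication continue assessments, but it does not clearly cover people who leave before induction.
5. For non-starters not reached, report the retained-diagnosis result beside a sensitivity analysis that varies their OUD probability by arm.
6. Reconcile abstract section 2.4 (Interventions) and sections 5.2, 7.2 and 7.4.1 on the order of challenge, eligibility and randomisation. No clinical rule is proposed here.

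**Cost.** Items 1, 2 and 5 are SAP wording. At the assumed 10-20% non-start in VI and PNV, item 4 means 100 × 0.10 to 100 × 0.20 = 10-20 visits without replacement. With arm-specific replacement it means about 111 × 0.10 to 125 × 0.20 = 11-25. At the $40 per assessment visit in section 7.15, that is roughly $400-1,000 in participant payments, plus the amendment, tracing, staff time and any visits in DE. Some non-starters will not be found, and including people who were never treated dilutes the estimated effect somewhat.

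Section 10.0 also contradicts itself on imputation of post-baseline data. That is a separate issue.

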2.4 Interventions

All participants will be scheduled for twice-monthly medical management and assessment appointments for the first three months of the 24-week post-release intervention phase, with monthly appointments for months 4-6. Eligible participants will be randomly assigned to treatment condition (VI, PNV, DE) in equal numbers. VI and PNV participants will undergo a naloxone challenge to ensure opioid abstinence at the time of Vivitrol induction. Those in the PNV condition will be provided with a PN who will facilitate attendance at outpatient treatment programs as well as assist with other needs. The DE group will not receive any medication but will be scheduled for assessments and education on drugs of abuse, maintaining abstinence, and methods for avoiding overdoses on the same schedule as the other two groups. The DE group will also be

provided with naloxone kits to be used in the event of overdose. All groups will also be provided with referrals to community-based substance abuse treatment programs.

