10.4.2 Primary Statistical Analysis of the First Primary Outcome Measure

A mixed effects logistic regression will used to model the binary primary outcome measure; the diagnosis of opioid use disorder at six months post treatment. are modeled as a linear combination of predictor variables. A logit link function will be used to link subject covariates to the probability of success There will be two levels in the model: within sites and between sites. The model will included treatment, cluster (site) and baseline covariates as fixed effects and subject as a random effect. Indicator variables will identify whether a subject has received XR-NTX, methadone and a behavioral intervention (PN.) Site by treatment interactions will be included in the model. Interactions that are statistically significant at the 10% level will be investigated and may imply that analyses of individual sites is required. In this case, relevant contrasts will be performed within the sites.

Additional covariates will include age, gender, whether a subject had prior methadone maintenance treatment and baseline self-reported cocaine use. Other possibilities mediating

factors include opioid dependence severity at baseline, concurrent cocaine or alcohol and/or benzodiazepine misuse, and homelessness.

SAS PROC Mixed will be used to perform the analysis. The coefficients in the model will be estimated by generalized least squares (GLS), with covariance parameters estimated by restricted maximum likelihood (REML). Standard errors of the parameter estimates will be computed using the model. This procedure assumes that missing observations are ignorably missing or missing at random (MAR).

The primary contrast is a comparison of the probability of a DSM-5 Opioid Use Disorder Diagnosis at 6 months for those on medication versus those receiving enhanced treatment as usual (etau.) The contrast will utilize XR NTX data from both the NYU and UCLA and Interim Methadone data from FRI; the medication plus PN treatment arm will not be included.

Descriptive statistics will examine feasibility issues of the pharmacotherapy, analyzing AEs, side effects, and patient and clinician acceptance, and reasons for early termination or post-randomization refusal of assigned condition. Single-point, between-group comparisons of these measures can be tested using t-tests or ANOVAs for continuous variables and chi-square for binary measures.

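### As worded, the plan lets arm membership in the main analysis depend on treatment received after randomisation; the primary model should code the randomised arm

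*Combined protocol and SAP*

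**What the plan says.** Three statements bear on which arm a participant is counted in.

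- **Section 10.0, PP grouping.** "Subjects in the PP population will be allocated to treatment groups in the analysis based on the actual treatment they received".
- **Section 10.0, switch rule.** If the ITT and PP populations differ substantially, "all analyses described below will be performed using only subjects in this group". The group meant reads as PP. The plan does not say how large a difference is substantial, or whether the difference is in membership or in results.
- **Section 10.4.2, primary model.** "Indicator variables will identify whether a subject has received XR-NTX, methadone and a behavioral intervention (PN", closing bracket omitted here. This is not limited to PP. The same paragraph says "The model will included treatment, cluster (site) and baseline covariates as fixed effects", without stating whether treatment there means assigned or received.

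Other text limits or extends the reach of these statements.

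- The ITT set in section 10.0 is built from "all randomized participants who received at least one dose of medication (VI, PNV), or received at least one session of drug education (DE", again without the closing bracket. No regrouping by treatment received is stated for it.
- The first PP exclusion applies where "concomitant medication that is known to have significant clinical effect on primary or secondary endpoints was administered".
- Section 10.4.2 sets the primary contrast as medication against enhanced treatment as usual and adds that "the medication plus PN treatment arm will not be included".
- Section 5.1 plans a first navigator meeting before discharge. No section says how much contact counts as having received navigation.
- Section 2.4 (Interventions) gives a route to outside treatment: "All groups will also be provided with referrals to community-based substance abuse treatment programs".

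**The concern.** Whether someone meets a navigator, or seeks medication in the community, is decided after randomisation and is likely to be related to relapse. If such behaviour sets the arm in which a person is analysed, the arms are no longer the ones randomisation made comparable. The trial is open-label (section 7.14), so blinding gives no further protection.

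PNV is VI plus the navigator. Under received-treatment indicators, a PNV participant with the injection but no counted navigator contact has the same codes as a VI participant. The outcome rule in section 10.0 could add to the effect. Dropouts are scored as retaining the diagnosis, so any non-engager who also drops out carries a failure from one arm to the other.

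The switch rule matters because it could carry the PP grouping into all analyses on a judgement that can be made after the results are seen.

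**Working it through.** The plan gives no figure for crossover or for its effect, so there is none to reproduce. The check sets out who could move, then how much a move would matter.

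**Who could move, reading the text literally**

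| Participant | Within PP | Outside PP, section 10.4.2 indicators |
|---|---|---|
| PNV, injected, judged not to have received navigation | Grouped as VI | XR-NTX yes, PN no: same codes as VI |
| DE, methadone or XR-NTX obtained in the community | Normally removed by the first PP exclusion | Coded as medicated |

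The PNV participant in the first row reaches the primary contrast only if the arm left out of it is also identified by treatment received. The text does not settle that.

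**Size of the PNV-to-VI move**

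From the plan: 50 per arm (section 10.3) and a two-sided 5% level (section 10.0). Assumed: no true effect of medication or navigation; a fraction f of each arm would not engage with a navigator; diagnosis risk at month 6 is 0.80 in those people and 0.50 in the rest.

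- Every arm as randomised: 0.5(1 − f) + 0.8f = 0.5 + 0.3f
- PNV after non-engagers are moved out: 0.50
- VI after they are moved in: (0.5 + 0.3f + 0.8f)/(1 + f)

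| f | DE, and VI as randomised | VI after the move | False PNV-VI difference | False VI-DE difference |
|---|---|---|---|---|
| 10% | 0.53 | 0.61/1.1 = 0.555 | −5.5 points | +2.5 points |
| 20% | 0.56 | 0.72/1.2 = 0.600 | −10.0 points | +4.0 points |
| 30% | 0.59 | 0.83/1.3 = 0.638 | −13.8 points | +4.8 points |

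PNV looks falsely better than VI, and VI looks falsely worse than DE. In simulation with a pooled two-proportion z-test, the false-positive rate for PNV-VI is about 9%, 17% and 27%, and for VI-DE about 6%, 7% and 8%. Analysed by assigned arm, PNV-VI stays at about 5 to 6%.

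**Other assumed inputs**

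Hold every arm at 50% diagnosed, and let 10-40% of PNV move with risk 60-80%.

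- Smallest case (10%, risk 0.6): PNV (0.5 − 0.06)/0.9 = 0.489; VI (25 + 3)/55 = 0.509; PNV-VI −2 points and VI-DE +1 point.
- Largest case (40%, risk 0.8): PNV (0.5 − 0.32)/0.6 = 0.300; VI (25 + 16)/70 = 0.586; PNV-VI −29 points and VI-DE +9 points.
- If those moved have the arm's average risk of 0.5, every group stays at 0.5 and the bias is zero.

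**DE participants coded as medicated (outside PP)**

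On the same 50% base, let 5-20% of DE move to the VI side with risk 30-70%. At 20% and risk 0.3, DE is (0.5 − 0.06)/0.8 = 0.550 and VI is (25 + 3)/60 = 0.467, so VI-DE is −8 points. At 20% and risk 0.7, DE is (0.5 − 0.14)/0.8 = 0.450 and VI is (25 + 7)/60 = 0.533, so VI-DE is +8 points. The sign is not predictable from the documents.

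**Would excluding non-engagers be enough?**

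In the first scenario, dropping PNV non-engagers from PP leaves PNV at 0.50 against VI at 0.53, 0.56 and 0.59. That is still a false PNV advantage of 3, 6 and 9 points, with false-positive rates of about 6%, 9% and 13%. Exclusion shrinks the bias but does not remove it.

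**The case against.** A reader might infer that treatment is coded as received throughout and that every arm comparison is therefore biased. The documents do not support that, for five reasons.

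- The regrouping sentence covers PP only. Section 7.3 counts those who terminate after induction or the first DE session as treatment failures in an intention-to-treat analysis.
- The section 10.4.2 indicators may be loosely worded arm coding. The contrast there pools XR-NTX data from two centres with interim methadone data from a third, and XR-NTX, methadone and PN look like the components of those studies' arms.
- The planned pre-discharge navigator meeting limits how many PNV participants have no contact. If that one meeting counts as receipt, few or none would move.
- Within PP, a DE participant medicated outside would normally be excluded, not counted as medicated.
- The larger figures are for PNV-VI, which is not the primary contrast, and they rest on an assumed difference in prognosis.

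All five stand as limits on the claim. They do not remove it. Nothing says that the indicators or the treatment term mean the assigned arm, receipt of navigation is undefined, and the switch rule can still put the PP grouping in place of ITT. Section 10.3 describes the trial as preliminary, which lowers the stakes, but the correction is only wording.

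**Conclusion.** The point holds in limited form. The plan prescribes grouping by treatment received within PP, allows PP to replace ITT on an undefined trigger, and words the primary model's indicators as treatment received. Followed literally, arm membership in the main analysis can depend on behaviour after randomisation. This can bias PNV-VI and medication-DE; it is not shown to bias every comparison.

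Size and direction depend on crossover rates and prognosis that the documents do not give. With 10-30% non-engagement and 80% against 50% risk, the false difference is about 5 to 14 points for PNV-VI and about 2 to 5 points for VI-DE, the latter against medication. With equal prognosis it is zero. The DE route applies only outside PP, and its sign is open.

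**What to change.** 1. **Section 10.4.2:** state that the treatment term and the XR-NTX, methadone and PN indicators are defined by randomised arm, whatever is later received, and that the arm left out of the primary contrast is identified in the same way.
2. **Section 10.0:** delete the sentence that lets PP replace ITT. Keep the PP or as-treated analysis only as a labelled sensitivity analysis. Excluding non-engagers instead of moving them is not a substitute, because it leaves part of the bias.
3. **Reporting:** define what counts as having received navigation for that sensitivity analysis, and tabulate navigator contacts and non-study opioid medication by randomised arm as descriptive data.

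The cost is a few sentences of analysis text and two descriptive tables. No added participants or visits are needed.

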2.4 Analyses

The primary outcomes include opioid use and DSM-5 diagnosis of opioid use disorder via modified CIDI-2 Substance Abuse Module at 6-months post-intervention. Opioid use will be computed from the Timeline Follow-Back (TLFB) as the number of days of self-reported opioid use in the past 30 days at the 6-month assessment. The cost analysis will measure and value resources associated with VI, including medical personnel (physician/nurses), labs, and medications. To ascertain cost-effectiveness ratios of VI and PNV, cost data will be compared to changes in key clinical measures of effectiveness.

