4.3.1 Primary Objectives

The primary objective is to compare outcomes of the three intervention groups, measured a The opioid use and DSM-5 diagnosis of opioid use disorder via modified CIDI-2 Substance Abuse Module at 6-months post-intervention.

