6.1 Primary Outcome Measure

The primary outcomes will be opioid use and a DSM-5 diagnosis of opioid use disorder 6 months after randomization.

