6.2 Secondary Outcome Measures

- HIV risk behaviors (compared using repeated measures procedures to evaluate possible change in sexual and drug-related behaviors that may inhibit or promote HIV infection) measured by the HIV-GAIN;
- (2) Self-reported number of days incarcerated during the intervention and follow-up phases;
- (3) Self-reported number of days of opioid and other drug use measured by TLFB, and objective measures of drug use by urine drug screens (UDS) at the 6-month post-release assessment (end of the intervention phase);
- (4) Self-reported days in drug abuse treatment;
- (5) Self-reported number of arrests;
- (6) Self-reported craving for opioids;
- (7) Self-reported number of overdoses; and
- (8) Self-reported motivation for treatment.

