7.3 Random Assignment

Eligible participants will be randomly assigned to study condition (VI, PNV, DE) in a 1:1:1 strategy using an urn randomization procedure (Stout et al., 1994) to provide multivariate balance across two characteristics correlated with outcomes in addiction treatment trials: type of opioid (heroin or prescription drug) and gender.

Individuals who terminate participation before induction onto the assigned medication (or similar time-point for behavioral assignments) will be replaced. Those terminating after VI induction or provision of the first DE session will not be replaced and will be counted as "treatment failures" (in an intent-to-treat scenario).

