10.1 Primary Outcome

The primary outcomes of opioid use and a DSM-5 diagnosis of opiate use disorder 6 months after randomization.

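### Two primary outcomes are each tested at two-sided .05 with no decision rule: about 7% to 9.75% risk of a false primary claim on the one named contrast, and more only if further arm pairs count as primary

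*Combined protocol and SAP*

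**What the plan says.** Section 6.1 states: "The primary outcomes will be opioid use and a DSM-5 diagnosis of opioid use disorder 6 months after randomization". Section 10.1 repeats it. Section 2.4 (Analyses) defines the first of the two: "Opioid use will be computed from the Timeline Follow-Back (TLFB) as the number of days of self-reported opioid use in the past 30 days", taken at the 6-month assessment.

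Section 10.0 sets the level: "All statistical tests will be performed using two-sided .05 significance levels, unless otherwise stated". The only other levels stated are 0.10 for baseline differences (10.4.1) and 10% for interactions (10.4.2). Neither governs a primary comparison.

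On arms, section 7.3 has participants "randomly assigned to study condition (VI, PNV, DE) in a 1:1:1 strategy", and section 4.3.1 says: "The primary objective is to compare outcomes of the three intervention groups". Section 10.4.2 is narrower. It names one primary contrast, for diagnosis only: medication against enhanced treatment as usual, which section 7.6.1 identifies with drug education (DE). The PNV arm is left out of it.

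On rank, the heading of 10.4.2 calls diagnosis the first primary outcome. Section 10.0 speaks of it in the singular: "For the primary outcome measure, diagnosis at six months, subjects who have dropped out for whatever reason will be considered to retain the diagnosis". No section gives a model or a contrast for the opioid-use outcome. Secondary outcome (3) in section 6.2 includes: "Self-reported number of days of opioid and other drug use measured by TLFB".

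**The concern.** With two primary outcomes, the plan has to say what makes the trial positive. If both must reach significance, testing each at .05 does not inflate the error rate. If either is enough, the error rate of the primary claim exceeds .05. The plan does not choose. It indicates a lead outcome but attaches no rule to it.

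The gap is wider for opioid use, because without a named contrast any of the three arm pairs could be presented as its primary comparison. The overlap with secondary outcome (3) adds a further freedom, since month-6 opioid-use days could be reported at either level. In an open-label trial these choices should be fixed before outcomes are compared by arm.

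**Working it through.** **Inputs.** Two-sided .05 per test (10.0). Two primary outcomes (6.1, 10.1). Three equal arms (7.3). One named contrast for diagnosis, without PNV (10.4.2). The plan states no error rate for the primary claim, so there is no figure of its own to reproduce. It also gives no correlation r between the two outcomes. I treat r as an assumption and show its range.

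**Set-up.** No effect of any arm on either outcome. Tests are approximated as z-tests with critical value 1.96. A false primary claim is at least one rejection among the tests counted as primary. Contrasts that share an arm are correlated, and the simulation (2,000,000 draws) carries this.

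**Closed form at r = 0.**
- One contrast on both outcomes: 1 − 0.95² = 9.75%.
- All three pairs on one outcome: 12.2% (simulated, because the pairs share arms).
- One contrast for diagnosis plus three pairs for opioid use: 1 − 0.95 × (1 − 0.122) = 16.6%.
- Three pairs on both outcomes: 1 − (1 − 0.122)² = 22.9%.

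**Simulated over r.**

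| Tests counted as primary | r = 0 | r = 0.5 | r = 0.9 | r = 1 |
|---|---|---|---|---|
| One contrast, both outcomes | 9.7% | 9.1% | 7.1% | 5.0% |
| Diagnosis on one contrast, opioid use on all three pairs | 16.6% | 15.9% | 13.9% | 12.2% |
| VI vs DE and PNV vs DE, both outcomes | 17.3% | 16.1% | 12.6% | 9.1% |
| All three pairs, both outcomes | 22.9% | 21.3% | 16.7% | 12.2% |

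The first row is closest to the plan's text. The second follows if the missing contrast for opioid use is read as leaving all pairs open. The last two need contrasts that 10.4.2 does not make primary for diagnosis.

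The contrast in 10.4.2 also draws on data from other sites. If those data enter only the diagnosis test, the two tests share less information and the result moves towards the r = 0 column.

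**The case against.** The strongest reply is that the plan already narrows the question. Section 10.4.2 names one primary contrast and excludes PNV, sections 10.0 and 10.4.2 mark diagnosis as the lead outcome, and section 10.3 says the study is meant for preliminary characterization ahead of a larger trial. Section 10.0 also asks for estimates and 95% intervals for all treatment comparisons. All of this stands. It lowers the weight of the point and rules out some larger figures, but none of it is a rule for what happens when one primary outcome is significant and the other is not.

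Three stronger readings are tempting, and the documents do not support them.

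- **An error rate of 20% or more.** A reader might infer this from the three-group objective in 4.3.1. It needs six primary tests, and 10.4.2 sets only one for diagnosis. Treating six tests as independent (1 − 0.95⁶ = 26.5%) overstates it further, because the contrasts share arms.
- **No ordering at all.** A lead outcome is indicated. What is missing is the testing rule.
- **The same variable listed as both primary and secondary.** Secondary outcome (3) gives no 30-day window, covers other drugs as well, and is timed from release, whereas 6.1 times the primary outcomes from randomization. It may be a different summary. That calls for clarification, not removal of the whole item.

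It can also be argued that diagnosis and days of use are so closely related that the inflation is slight. High correlation is plausible, but at 0.9 the one-contrast figure is still 7.1%. The two outcomes also handle dropouts differently in 10.0: retained diagnosis for one, multiple imputation for other measures. With 10–20% dropout expected (10.3), a correlation near 1 is unlikely.

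**Conclusion.** The concern holds in a limited form. Two outcomes are primary, each is tested at .05, and no decision rule links them. If success on either counts, the false-claim rate is about 7% to 9.75% for the named contrast applied to both outcomes (r from 0.9 to 0), and 5% only at r = 1. It is about 14% to 17% if all pairs stay open for opioid use. The range of about 17% to 23% applies only if all pairs are primary on both outcomes, which the plan does not set for diagnosis.

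These figures rest on an assumed correlation, normal approximations, and the either-outcome reading, which the plan neither adopts nor excludes. Given the stated preliminary purpose, this should be fixed, but it is not a fatal defect.

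**What to change.** 1. Test the month-6 diagnosis first, on its single named primary contrast, at two-sided .05. Only if it is significant, test month-6 opioid-use days on the same contrast at .05. This holds the error rate of the primary claim at 5% and costs the diagnosis comparison no power.
2. Report all other arm pairs and outcomes with estimates and 95% intervals, and make no confirmatory claim from them.
3. If VI vs DE and PNV vs DE are both to be confirmatory, run a separate diagnosis-then-opioid-use sequence for each contrast at .025. The total error is then at most .025 + .025 = .05. A step-down procedure across contrasts combined with an outcome order would also need its gate written out, and separate sequences avoid that.
4. In secondary outcome (3), state that month-6 past-30-day opioid-use days are the primary variable. Keep other drugs, urine screens and any different opioid summary as secondary.

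**Cost.** Opioid-use days cannot be claimed as confirmatory if the diagnosis comparison fails. Option 3 also costs power. As an illustration on a continuous outcome with 40 evaluable per arm, power ≈ Φ(d√(n/2) − z):
- d = .6: Φ(2.683 − 1.960) = 76.5% at .05, against Φ(2.683 − 2.241) = 67.1% at .025.
- d = .5: Φ(2.236 − 1.960) = 60.9% at .05, against Φ(2.236 − 2.241) = 49.8% at .025.

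The .05 values differ from the power quoted in 10.3. That is a separate matter and does not affect the error rates above.

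The change is mostly wording, but two items must be settled first: a model and contrast for opioid-use days, and whether the gate uses this trial's data alone or the pooled data described in 10.4.2. Both should be fixed before any month-6 outcome is compared by arm.
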